9.3 Justification for the Sample Size

The point estimate of the ORR with nivolumab in combination with ipilimumab in this patient population is 40%, based on the Phase I presented at ASCO meeting which is chosen as the reference rate (P0) in the study proposed. The response rate where the regimen would be considered promising to pursue further is 70% (P1). In the first stage,

responses will be evaluated on the first 15 subjects treated. If 6 or fewer responses are observed after 6-18 weeks of follow-up, the study will be terminated for futility. Otherwise, 10 additional subjects will be accrued to target a total of 25 treated subjects. During the evaluation of response in the first stage, we will continue the recruitment and treatment of subjects. This design has at least a 90% chance (power) of concluding the combination therapy is effective when the true response rate is 70% and a 5% chance (Type I error) of concluding the treatment is effective when the true response rate is 40% or less. The probability of stopping early is 61% if the true response rate is 40% or less and 1.5% if the true response rate is 70%. The null hypothesis will be rejected and the regimen will be declared a success if at the end of the study 17 or more responses are observed in 25 treated subjects. The anticipated accrual rate for this group of patients is expected to be 2 patients per month.

Early Stopping Guidelines for Safety: The safety profile of the combination of SBRT with dual immune checkpoint inhibition using nivolumab and ipilimumab is not yet established, and therefore we will conduct continuous toxicity monitoring after safety run-in to ensure this combination is safe. If the risk of Grade 3/4 adverse events convincingly exceeds 50%, a threshold we are comfortable given the potential benefit of the regimen as well as our experience in managing the side effects in this patient population, we will temporarily halt the study and carefully review the available data at that point in order to suggest potential modification of the combination regimen. Specifically, a Bayesian toxicity monitoring rule will suggest suspending enrollment if the posterior probability of risk being larger than 0.50 is 75% or higher. The prior for this monitoring rule is beta (1, 2), representing the risk of DLT has mean of 33% and there is 90% probability that this risk is between 2.5% and 78%. The stopping rules for safety and the operating characteristics based on 5000 simulations are as below.

No. patients experiencing G3/4 AE/steroid needs	6	7	8	9	10	11	12	13	14	15
	Out of	7-8	9-10	11-12	13-14	15-16	17	18-19	20-21	22-23
True risk of AE				Prob. declaring regimen too toxic				Avg. sample size		
0.30				2.1%				24.7		
0.40				12.8%				23.3		
0.50				38.5%				20.1		
0.60				71.3%				15.6		
0.65				85.3%				13.2		
0.70				94.6%				10.9		

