This material is the property of the [UTSW Simmons Cancer Center](#). Do not disclose or use except as authorized in writing by the study sponsor.

Per a study amendment, the N3 + I1 and N1 + I3 arms were expanded to better evaluate safety and efficacy. Mature efficacy data was presented at ASCO 2015. The confirmed ORR was 38.3% (N3 + I1) and 40.4% (N1 + I3). Best response of SD was achieved in 36.2 % of patient in both treatment arms. Median DOR was 67.7 weeks (range 4.1+ to 91.1+) in the N3 + I1 arm and 81.1 weeks (range 6.1+ to 81.1+) in the N1 + I3 arm. Responses were durable, with >60% of patients continuing to experience ongoing response. The PFS rate (95% CI) at 24 weeks was 54% (39–68) in the N3 + I1 arm (N = 47) and 68% (52–79) in the N1 + I3 arm (N = 47). Median OS was not reached in either the N3 + I1 arm or in the N1 + I3.¹⁸

Table 1. ORR and best Overall Response

	NIVO3 + IPI1	NIVO1 + IPI3	NIVO3 + IPI3
	N = 47	N = 47	N = 6
Confirmed ORR ^a , n (%) 95% CI	18 (38.3) 24.5–53.6	19 (40.4) 26.4–55.7	0
Best overall response ^b , n (%)			
Complete response	4 (8.5)	1 (2.1)	0
Partial response	14 (29.8)	18 (38.3)	0
Stable disease	17 (36.2)	17 (36.2)	5 (83.3)
Progressive disease	10 (21.3)	7 (14.9)	1 (16.7)

^aConfirmed response only; ^bNo unconfirmed complete responses were reported in either arm; unconfirmed partial responses were reported in one patient (2.1%) in the NIVO3 + IPI1 arm and in two patients (4.3%) in the NIVO1 + IPI3 arm. Best overall response was not determinable in one patient (2.1%) in the NIVO3 + IPI1 arm and in two patients (4.3%) in the NIVO1 + IPI3 arm.

Grade 3–4 related AEs occurred in 36 pts, including 16/47 (34%) at N3 + I1 and 30/47 (63.8%) at N1 + I3. The most common (≥20%) drug-related Grade 3-4 events were lipase increased including 6/47 (12.8%) at N3 + I1 and 12/47 (25.5%) at N1 + I3; ALT increased including 2/47 (4.3%) at N3 + I1 and 4/47 (8.5%) at N1 + I3 and diarrhea including 1/47 (2.1%) at N3 + I1 and 7/47 (14.9%) at N1 + I3. Grade 3-4 colitis was observed in 6/47 (12.8) at N1 + I3 only. No grade 3–4 pneumonitis was seen. No treatment-related deaths were reported. Treatment-related AEs (including Grade 3-4), treatment-related AEs leading to discontinuation, and treatment-related SAEs all occurred more commonly in subjects in the N1 + I3 arm than in the N3 + I1 arm.¹⁸

Table 2. Treatment-related Select AEs^{a,b}

Category, n (%)	NIVO3 + IPI1		NIVO1 + IPI3		NIVO3 + IPI3	
	N = 47		N = 47		N = 6	

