stage. If 6 or less achieve an objective response, then the response data will be reviewed carefully and study termination will be discussed. If a number of patients have near partial responses or evolving tumor shrinkage the team may decide to continue with accrual to get a larger sample size. If 7 or more patients have an objective response, then the second stage will proceed automatically with additional 10 patients. If a total of 17 or more patients respond, we will conclude this regimen is promising and warrants further study.

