4.6.2 Response Criteria

Subjects will be evaluated for tumor response beginning 6 weeks *from treatment and continuing every 6 weeks (± 1 wk) for the first 13 months from treatment and every 12 weeks (± 1 wk) thereafter*, until disease progression is documented or treatment is discontinued (whichever occurs later).

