4.6.9 Evaluating best overall response

The best overall response is the best response recorded from the start of treatment until either disease progression or recurrence. The investigator's determination of best overall response will be based both on response criteria and on confirmation criteria. To be assigned a status of partial response or complete response, changes in tumor measurements must be confirmed by repeat assessment performed at least 6 weeks after the criteria for response are first met. To confirm stable disease, follow-up measurements must meet SD criteria at a minimum interval of 6 weeks after SD was first documented. Table 9 can be used as an assessment tool.

Table 9. Assessing Overall Response

Target Lesions	Non-target Lesions	New Lesions	Overall Response
CR	CR	No	CR
CR	Incomplete response/SD	No	PR
PR	Non-PD	No	PR
SD	Non-PD	No	SD
PD	Any	Yes or No	PD
Any	PD	Yes or No	PD
Any	Any	Yes	PD

Abbreviations: CR, complete response; PD, progressive disease; PR, partial response; SD, stable disease.

STU072016-044, [name], FormA-ResearchProtocol-V7.0-09.30.19, Mod_14, 10-23-19 (2)

Page 60 of 99 (BMS CA209-444) V. V6.0 date March 1, 2019

This material is the property of the [UTSW Simmons Cancer Center](#). Do not disclose or use except as authorized in writing by the study sponsor.

Patients with global deterioration of health status who require treatment to be discontinued without objective evidence of disease progression should be classified as having symptomatic deterioration. Every effort should be made to document their objective progression, even after discontinuing treatment.

Patients who do not have tumor response assessment due to rapid progression or toxicity will be considered non-responders, will be included in the denominator for the response rate, and will be classified into one of the categories listed below:

- death attributed to disease progression
- early discontinuation attributed to disease progression
- death attributed to drug toxicity
- early discontinuation attributed to drug toxicity

Note: If a patient receives subsequent therapy before tumor progression is documented, the reason for changing therapy must be reported. Reasons include clinical progression, drug toxicity, or secondary therapy for maintaining tumor response.

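### Sections 2.1 and 9.3 give different actions for 6 or fewer responses in the first 15, and 9.3 dates that count only by a 6-18 week range that partly precedes any confirmed response

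*Combined protocol and SAP*

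**What the plan says.** Stage 1 enrols 15 patients, and the threshold is 6 or fewer responses.

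- **Section 9.3** prescribes the action: "If 6 or fewer responses are observed after 6-18 weeks of follow-up, the study will be terminated for futility". It adds that "The probability of stopping early is 61% if the true response rate is 40% or less" and gives 1.5% at a true rate of 70%. Recruitment stays open during the evaluation, at an expected 2 patients per month.
- **Section 2.1 (Efficacy phase)** says of the same result that "the response data will be reviewed carefully and study termination will be discussed". It continues: "If a number of patients have near partial responses or evolving tumor shrinkage the team may decide to continue with accrual".
- **Section 4.6.2** sets the scan schedule: "Subjects will be evaluated for tumor response beginning 6 weeks" from treatment, then every 6 weeks, each with a 1-week window.
- **Section 4.6.9** says that a change qualifying as CR or PR "must be confirmed by repeat assessment performed at least 6 weeks after the criteria for response are first met". Section 4.6.10 repeats this and accepts the next scheduled scan as the confirmation.
- **Section 9.4** defines ORR as CR/PR by RECIST, without the word confirmed.
- **Section 1.4** reports the Phase I rates behind the 40% reference as confirmed ORR: 38.3% and 40.4% in the two expanded arms.

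**The concern.** A team holding 6 of 15 responses can cite 9.3 to close the trial or 2.1 to continue it. Both are current text, and this is the trial's only efficacy stop. The stopping probabilities in 9.3 therefore do not describe one agreed rule.

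The second difficulty is when responses are counted. Section 9.3 gives a range of follow-up, does not say whose follow-up it is, and does not mention confirmation. If the count is made near the early end, the most recently enrolled patients cannot yet be confirmed responders, and a binding stop would treat them as failures. An active regimen could then be stopped more often than the plan states. The discretion in 2.1 would protect late responders, but 9.3 does not contain it.

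**Working it through.** **Inputs.** From 9.3: 15 patients in stage 1, stop at 6 or fewer, 25 in total, success at 17 or more, reference rate 0.40, target rate 0.70, 2 patients per month. From 2.2: enrolment of 3-6 plus 18 months, so 25 patients over 21-24 months (1.04-1.19 per month). From 4.6.2 and 4.6.9: first scan at week 6 (±1), confirmation at least 6 weeks later. One month is taken as 4.345 weeks.

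**1. The plan's own figures.** P(Bin(15, 0.40) ≤ 6) = 0.6098 and P(Bin(15, 0.70) ≤ 6) = 0.0152. The stated 61% and 1.5% reproduce. However, 9.3 attaches 61% to every rate of 40% or less, and it holds only at exactly 40%: the same formula gives 0.66 at 38.3% and 0.87 at 30%.

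**2. If the discretion in 2.1 is used, final status known.** Let q be the share of stop signals that are acted on. At a 40% rate, P(stop) = q × 0.6098 and expected N = 15 + 10 × (1 − q × 0.6098):

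- q = 1: 18.9
- q = 0.5: 21.95
- q = 0: 25

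This is before counting patients enrolled during the evaluation. A trial continued with 6 responses can reach at most 6 + 10 = 16, which is below 17. The probability of declaring success is therefore the same with and without the stop: 0.0043 at 40% and 0.677 at 70%. (That 0.677 differs from the stated 90% power is a separate matter.)

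**3. Earliest confirmed response.** 6 + 6 = 12 weeks, or 5 + 6 = 11 weeks if the first scan uses the early window.

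**4. If 9.3 is binding and counts confirmed responses only.** Assume evenly spaced accrual, and that every eventual response in patients past 12 weeks is already confirmed. Let k be the number of patients under 12 weeks when the count is made.

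- Patient 15 at week 6, 2 per month (spacing 2.17 weeks): the latest patients stand at 6, 8.2, 10.3 and 12.5 weeks, so k = 3.
- Patient 15 at week 6, slower accrual (spacing 3.65-4.17 weeks): 6, 9.6-10.2 and 13.3-14.3 weeks, so k = 2.
- Patient 15 at week 18: nobody is under 12 weeks, so k = 0.

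An 11-week threshold gives the same k. The chance of meeting the stop rule is P(Bin(15 − k, p) ≤ 6):

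| k | p = 0.40 | p = 0.70 |
|---|---|---|
| 0 | 0.610 | 0.015 |
| 2 | 0.771 | 0.062 |
| 3 | 0.842 | 0.118 |

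**5. Cost of a later count with accrual open, at a 40% rate.** With a patients enrolled during the evaluation and stopping probability s, expected N = 25 − s × (10 − a), where a = rate × weeks / 4.345.

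- 2 per month, week 18 (a = 8.29, s = 0.6098): about 24.0.
- 2 per month, week 6 (a = 2.76): 18.9 with s = 0.8418, 20.6 with s = 0.6098.
- Slower accrual, week 18 (a = 4.32-4.93, s = 0.6098): 21.5-21.9.
- Slower accrual, week 6 (a = 1.44-1.64): 18.4-18.6 with s = 0.7712, 19.8-19.9 with s = 0.6098.

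**The case against.** The strongest reply has four parts.

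- **Confirmation is already defined.** This stands. Sections 4.6.9 and 4.6.10 do not assign CR or PR until a repeat scan, and 9.4 counts CR/PR. A reader might infer that the protocol never settles whether unconfirmed responses count, and the documents do not support that. What is missing is the link from 9.3. Once the rule is applied, the early end of the 9.3 range cannot yield the endpoint for the newest patients.
- **The larger probabilities are one end of a range.** This also stands. A reader might take 11.8% as the trial's false-stop rate. It requires a binding stop, a count when patient 15 is at week 6, accrual at 2 per month and confirmed responses only. A count when patient 15 reaches week 18 is equally within the wording and gives back 1.5% and 61%.
- **Discretion over a futility stop is harmless to the error rates.** Correct under the 17 of 25 rule. A reader might infer that the override in 2.1 inflates type I error, but it does not (step 2). Nor is a stopping probability of 0% to be expected: 2.1 ties continuation to signs of shrinkage, so q = 0 is a limit.
- **A week-18 cut-off does not give final status.** True. A response first seen at week 18 is still unconfirmed, and later responses are missed. Week 18 is one reasonable choice, not the only one.

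None of this removes the conflict between the two sections or supplies a single count date.

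**Conclusion.** The point holds. Sections 2.1 and 9.3 prescribe different actions for the same stage 1 result, and the range in 9.3 includes times at which some of the 15 cannot have a confirmed response. The 61% (at exactly 40%, higher below) and 1.5% (at 70%) are valid only for a binding stop with final status known in all 15.

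The size depends on which text is followed:

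- Under 2.1, stopping at a 40% rate is at most 61%, and expected N is between 18.9 and 25 before accrual during the evaluation. With final status known, type I error and power under 17 of 25 are unchanged.
- Under a binding 9.3 stop on confirmed responses, the chance of meeting the rule is 1.5% with a late count and 6.2-11.8% with an early count at a 70% rate. At 40% it is 61% and 77-84%.

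These ranges rest on evenly spaced accrual and on all other eventual responses being confirmed by the count. What is affected is the stopping probability, expected sample size and possible false stopping of an active regimen, not the false-positive rate.

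**What to change.** - Put one identical stage 1 rule in 2.1 and 9.3, and state whether the stop is binding or non-binding.
- Replace the 6-18 week range with one count date late enough for a confirmed response in all 15. For example: when each patient has completed the week-18 scan, has a confirmed response, or can no longer respond (progressed, died or ended tumor assessment). Stopping treatment alone should not close a patient's status, because 4.6.2 continues scans until the later of progression and treatment discontinuation.
- Cross-refer to 4.6.9 and 4.6.10 so that confirmed CR/PR is counted, as in the source of the 40% reference. Say how a response first seen at the last scan before the cut-off is treated.
- Allow an earlier decision once it is certain: 7 confirmed responses, or 15 − 6 = 9 patients who can no longer respond.
- Restate 61% as the value at a true rate of exactly 40%, and 1.5% at 70%, for a binding stop with final status known. If the stop is non-binding, call them maximum stopping probabilities at those rates.

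The cost is wording in two sections, plus a later count while accrual stays open. At 2 per month and a 40% rate, a week-18 count gives expected N of about 24.0, against about 18.9 to 20.6 with a week-6 count (84% or 61% stopping). About 8 of the 10 stage 2 patients would be enrolled by then, so a stop spares about 2. At the slower accrual rate expected N is 21.5-21.9, against about 18.4 to 19.9. Deciding as soon as the outcome is certain reduces this cost.

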9.1 Study Design

This is a multi-institution, open-label, single-arm Phase II study to determine the safety and efficacy of SBRT followed by nivolumab in combination with ipilimumab in patients with metastatic RCC. The primary endpoints of safety evaluated by the level of G3/4 treatment related adverse events and the need for corticosteroids in this patient population and ORR assessed by RECIST criteria. Secondary endpoints include TTP, DOR, PFS, OS and local control of irradiated lesion. Simon's minimax two-stage design will be used to allow for early termination of the study if addition of SBRT to nivolumab in combination with ipilimumab is unlikely to be promising. A safety run-in phase will be included in the first 6 patients, and safety will be monitored continuously after this safety run-in phase using a Bayesian posterior probability approach.

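### Requiring 17 of 25 responses for success gives about 68% power and 0.4% type I error, not the stated 90% and 5%; 15 of 25 fits the stated figures

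*Combined protocol and SAP*

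**What the plan says.** Section 9.3 bases the sample size on two response rates. The reference rate for nivolumab plus ipilimumab "in this patient population is 40%, based on the Phase I presented at ASCO meeting which is chosen as the reference rate (P0"). The target is 70%: "The response rate where the regimen would be considered promising to pursue further is 70% (P1").

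The design is described in Section 9.1: "Simon's minimax two-stage design will be used to allow for early termination of the study". In stage 1, "responses will be evaluated on the first 15 subjects treated", and "If 6 or fewer responses are observed after 6-18 weeks of follow-up, the study will be terminated for futility". Otherwise 10 more patients are added, for a total of 25. At the end, the regimen is "declared a success if at the end of the study 17 or more responses are observed in 25 treated subjects".

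For this rule, Section 9.3 states: "This design has at least a 90% chance (power) of concluding the combination therapy is effective when the true response rate is 70" per cent. It also states a type I error of 5% at a response rate of 40% or less, and early-stopping probabilities of 61% at 40% and 1.5% at 70%.

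Section 2.1 repeats the threshold: "If a total of 17 or more patients respond, we will conclude this regimen is promising and warrants further study". It differs from Section 9.3 on stage 1, because it lets the team continue after 6 or fewer responses if tumours are shrinking. Neither section gives a reason for a final bar stricter than the stated error rates require.

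**The concern.** Seventeen of 25 is an observed response rate of 68%, only just below the 70% the trial is meant to detect. When the cut-off sits that close to the target rate, a regimen that truly reaches the target will often miss it by chance, so 90% power is implausible on its face.

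This rule decides the primary efficacy endpoint. If its real power is well below the stated figure, a regimen as active as the sponsor hopes has a substantial chance of being dropped, and anyone relying on Section 9.3 is misinformed about that risk.

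**Working it through.** **Inputs** (Section 9.3): p0 = 0.40; p1 = 0.70; stage 1 of n1 = 15, stopping if 6 or fewer respond; stage 2 of 10 more patients; n = 25; success if total responses ≥ c, with c = 17.

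**Step 1: the plan's own stage 1 figures.** The early-stopping probability is P(X1 ≤ 6), with X1 ~ Bin(15, p).
- p = 0.40: 0.6098 (stated 61%)
- p = 0.70: 0.0152 (stated 1.5%)

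Both reproduce, so the inputs and the stage 1 rule have been read as intended.

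**Step 2: probability of declaring success.**

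P(success) = Σ over x = 7,…,15 of P(X1 = x) × P(X2 ≥ c − x), with X1 ~ Bin(15, p) and X2 ~ Bin(10, p).

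For c = 17 and p = 0.70:

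| x in stage 1 | P(X1 = x) | Needed in next 10 | P(X2 ≥ needed) | Product |
|---|---|---|---|---|
| 7 | 0.0348 | 10 | 0.0282 | 0.0010 |
| 8 | 0.0811 | 9 | 0.1493 | 0.0121 |
| 9 | 0.1472 | 8 | 0.3828 | 0.0564 |
| 10 | 0.2061 | 7 | 0.6496 | 0.1339 |
| 11 | 0.2186 | 6 | 0.8497 | 0.1858 |
| 12 | 0.1700 | 5 | 0.9527 | 0.1620 |
| 13 | 0.0916 | 4 | 0.9894 | 0.0906 |
| 14 | 0.0305 | 3 | 0.9984 | 0.0305 |
| 15 | 0.0047 | 2 | 0.9999 | 0.0047 |

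The products sum to 0.677. The stated power is at least 0.90.

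**Step 3: other final thresholds**, same stage 1 and n = 25:

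| Success if responses ≥ | Type I error (p = 0.40) | Power (p = 0.70) |
|---|---|---|
| 14 | 7.49% | 95.09% |
| 15 | 3.40% | 90.04% |
| 16 | 1.31% | 81.02% |
| 17 (plan) | 0.43% | 67.69% |
| 18 | 0.12% | 51.18% |

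Only 15 keeps type I error at or below 5% with power of at least 90%. At 14 the type I error is too high; from 16 upwards the power is too low.

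**Step 4: does the optional continuation in Section 2.1 matter?** With 6 responses in stage 1, the most a patient group can reach is 6 + 10 = 16. Success at 17 is then impossible, so treating the futility rule as non-binding leaves the figures for 17 unchanged (0.43% and 67.69%). For 15 they become 3.44% and 90.22%.

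**Step 5: what rate would 17 detect with 90% power?** Power at c = 17 is 87.7% at a true rate of 76% and 90.1% at 77%. The written rule is therefore powered for about 77%, not 70%.

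**The case against.** The strongest objection is that the documents prove an inconsistency, not which side of it is wrong. The threshold of 17 appears in two sections, whereas the power and type I error appear once. The 3.4% type I error at 15 of 25 equals the stated 5% only if 5% is read as a ceiling. Nor is 15 of 25 the strict minimax design for these error rates: stopping at 4 or fewer of 10 and requiring 14 of 24 gives 4.82% and 90.09% with one patient fewer. So 15 is the natural repair, but it cannot be shown to be the number the sponsor first calculated. That stands as a caution about origin. It does not rescue 17: a discrete design normally sits below its nominal alpha, and 17 misses the power claim however 5% is read.

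Lowering a success bar late in an open-label, single-arm trial could also look like a post hoc relaxation. The documents do not say whether response data had been reviewed. This stands, and it decides which correction is suitable.

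The error is also conservative. False-positive risk falls, and Section 9.4 reports the response rate with a confidence interval whatever the verdict. This limits the harm to lost power. It does not make the stated power true.

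Finally, a result of 15 of 25 has a two-sided 95% exact interval of 38.7% to 78.9%, which includes 40%; at 16 of 25 the lower limit is 42.5%. This comes from pairing a one-sided 5% rule with a two-sided 95% interval. It is not an error, but it should be disclosed.

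**Conclusion.** The concern holds. The written rule has 67.7% power against a stated minimum of 90%, a shortfall of about 22 percentage points, and a type I error of 0.43% against a stated 5%. At a true response rate of 70%, the risk of wrongly rejecting the regimen is 32.3% (100 − 67.7), not at most 10%. Final counts of 15 or 16 of 25 (60% or 64%) would be called failures, although a rule with the stated properties would call them successes.

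The calculation assumes independent patients with a common response rate and a full 25 evaluated if stage 2 opens. It uses only the plan's own inputs and does not depend on whether the futility rule is binding. It shows that the threshold and the stated error rates cannot both be right.

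**What to change.** First establish whether any response data have been reviewed. Then make one of two changes, identically in Sections 2.1 and 9.3:

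- **If they have not:** replace 17 or more with 15 or more of 25. State the exact properties: type I error 3.4%, power 90.0%, early stopping 61.0% at a 40% response rate and 1.5% at 70%. Note in Section 9.4 that 15 of 25 meets the success rule although its two-sided 95% interval includes 40%.
- **If they have, and moving the bar is not acceptable:** keep 17 and restate power as 68% and type I error as 0.4%. It would help to add that 90% power is reached only at a true rate of about 77%.

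If 15 of 25 is adopted, describe it as a Simon-type two-stage design with the stated boundaries, since a 24-patient design also meets the limits.

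The cost is wording in two sections (plus the interval note if 15 is adopted), processed as a protocol amendment with ethics approval. No patients, visits or assessments are added.
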